19.6 Secondary outcome analysis

Each of the secondary endpoints will be analysed with the null hypothesis that the IMP and placebo are similar for the primary endpoint.

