11.5 Objectives and Endpoints Summary

Objective	How objective measured	Outcome
Examine the effect of AZD1656 on Treg cell migration	Change in peripheral Treg population between randomisation and month 3 measured by mean change in Treg cell number between baseline and 3 months using FACS analysis.	Does AZD1656 lead to enhanced migration as demonstrated by a fall in peripheral Treg population over time compared to placebo?
Examine the effectiveness of AZD1656 on diabetic control	Change in HbA1c between baseline and month 3 visit, HOMA-IR at month 3, descriptive change in anti diabetic medication dose/need for additional anti-diabetic therapy.	Is there a difference between placebo and IMP on diabetic control/insulin resistance?
To investigate the effect of AZD1656 on renal transplant function	Renal function (eGFR CKD EPI) measured at 3 months and 12 months.	Is there a difference between AZD1656 and placebo treated patients' renal function at 3 and 12 months?
To determine the safety of AZD1656 to control diabetes post- transplant.	Patient and graft survival, number and type of AE (hypoglycaemic episodes, infective episodes), number and type of SAE, rejection rates (defined as incidence of biopsy proven acute rejection)	Is there a difference between placebo and AZD1656 treated groups in terms of number of AE, SAE, renal function and rejection rates?
Effect of AZD156 on Treg cell infiltration in renal transplant tissue	Change in Treg staining on renal biopsies collected as standard of care at implantation and 3 months post transplant.	Is there a difference between placebo and AZD1656 treated groups in terms of change in Treg cell infiltration between baseline and 3 month transplant biopsy?

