19.0 Statistical and Data Analysis

19.1 Sample size calculation

n=25 in each arm. This is a pilot/exploratory study: the numbers were chosen as this was felt to be feasible given the resources of the site, and will enable generation of data for a larger scale trial should the results of this pilot be encouraging.

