19.3 Statistical analysis plan (SAP)

Please refer to SAP for full details

Primary Endpoint

The primary endpoint is the change in mean peripheral Treg cell number between baseline and 3 months measured using FACS analysis between AZD1656 and placebo.

This will be analysed at the first data analysis.

Secondary Endpoints:

- 1) Histological staining for Treg cells in renal biopsy tissue between baseline and 3 month protocol biopsy
- Incidence of delayed graft function, defined as the need for dialysis within 1 week post-transplant
- 3) Diabetic control between baseline and month 3 using change in HbA1c measurement
- 4) Dose of other anti-diabetic medication between baseline and month 3 (descriptive)
- 5) Safety endpoints i.e. number of hypoglycaemic episodes (descriptive)
- 6) Insulin resistance: HOMA IR measurement at month 3
- 7) Graft function: (eGFR) at month 3
- 8) Episodes of acute rejection (defined as biopsy proven acute rejection)
- 9) Episodes of opportunistic infections: bacterial and viral (descriptive)

All of these endpoints will be analysed at the first data analysis; endpoints 8 and 9 will also be re-examined at the second data analysis.

Exploratory or Tertiary Endpoints/outcomes

- 1) 12-month graft function (eGFR) and diabetic control (HbA1c; medication review) to assess legacy effect (potential follow up publication)
- 2) Differences in other peripheral T cell populations, measured by FACS analysis
- 3) Histological staining for Treg cells in any renal biopsy taken for clinical indications between baseline and month 3 protocol biopsy
- 4) Differences in the functional phenotype of the Treg cells

Endpoints 2 and 3-4 will be analysed at the first data analysis; endpoint 1 will be analysed at the second data analysis.

Baseline Demographics and Biochemical parameters

Demographics and Clinical Characteristics

- Age at recruitment (derived from date of birth; continuous)
- Sex (categorical)
- Self-reported ethnicity (using ONS categories; categorical)
- Weight (continuous)
- Systolic BP (continuous)
- Diastolic BP (continuous)

Medical History

- Cause of end stage renal failure (categorical)
- Dialysis modality (categorical)
- Dialysis vintage (continuous)
- Diabetes duration (continuous)
- Retinopathy (yes/no, categorical)
- Neuropathy (yes/no, categorical)
- Coronary artery disease (yes/no, categorical)
- Peripheral artery disease (yes/no, categorical)
- Cerebrovascular disease (yes/no, categorical)

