19.5 Primary outcome analysis

The endpoint data will be analysed on an ITT basis, with no subgroup analysis using unpaired parametric and non-parametric analysis as necessary, comparing the

change in mean Treg cell number between baseline and month 3 between the 2 groups.

Continuous variables will be tested for normality using D'Agostino-Pearson normality test. Mean (standard deviation), median (interquartile ranges) will be displayed along with max-min point estimate and confidence intervals. Statistical analysis will be by student t-test (unpaired) or Mann-Whitney U test.

Categorical data will be analysed by Chi Square test.

Statistical significance considered if P-value <0.05.

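### Section 19.6 sets the wrong null for the secondary endpoints; separately, the protocol states only a chi-square P-value for delayed graft function and rejection, with no effect estimate, interval or small-count method

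*Combined protocol and SAP*

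**What the plan says.** Section 19.6 consists of one sentence: "Each of the secondary endpoints will be analysed with the null hypothesis that the IMP and placebo are similar for the primary endpoint". Section 19.3 defines the endpoint it points to: "The primary endpoint is the change in mean peripheral Treg cell number between baseline and 3 months measured using FACS analysis between AZD1656 and placebo".

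Section 11.3.2 lists nine secondary endpoints. Endpoints 4 (other anti-diabetic medication), 5 (hypoglycaemic episodes) and 9 (opportunistic infections) are labelled descriptive. The other six are not: Treg staining (1), delayed graft function (2), HbA1c (3), HOMA-IR (6), eGFR (7) and biopsy-proven acute rejection (8).

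Tests are named only in section 19.5, which is headed as the primary analysis. It says "Categorical data will be analysed by Chi Square test" and "Statistical significance considered if P-value <0.05". Its one mention of intervals is in the paragraph on continuous variables: "Mean (standard deviation), median (interquartile ranges) will be displayed along with max-min point estimate and confidence intervals".

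Section 11.5 treats rejection as an incidence under the safety objective and asks: "Is there a difference between placebo and AZD1656 treated groups in terms of number of AE, SAE, renal function and rejection rates". Section 19.1 gives the size and purpose of the trial: "n=25 in each arm. This is a pilot/exploratory study: the numbers were chosen as this was felt to be feasible"; the study "will enable generation of data for a larger scale trial should the results of this pilot be encouraging". Section 19.3 refers to a SAP for full details. No separate SAP text was available.

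**The concern.** There are two independent problems.

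**The null.** A test of HbA1c, eGFR or rejection needs a hypothesis about that outcome. Section 19.6 supplies one about Treg change instead. Because it is the whole of the secondary analysis section, nothing else there corrects it.

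**The binary endpoints.** The primary endpoint is continuous, so the chi-square sentence in 19.5 can only matter for other variables. Among the tested secondary endpoints these are delayed graft function and, read as an incidence, rejection. For both, the protocol text stops at a P-value. It names no risk difference or ratio, no interval, and no method for sparse tables. A pilot intended to inform a larger trial has to pass on arm-level rates and the range of differences that the data allow. A bare P-value from 25 per arm does not give that range, and with few events its position relative to 0.05 can depend on which version of the test is run.

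**Working it through.** **Inputs.** 25 per arm (19.1); two-sided alpha 0.05 (19.5; sidedness is not stated, so two-sided is assumed). The sample size rests on feasibility, so there is no power figure to reproduce. Placebo event rates are not in the documents; 5% to 20% is assumed. All splits below are AZD1656 v placebo and are illustrative.

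**Step 1: which endpoints the misworded null affects.** Nine listed, less three descriptive, leaves six. None of the six is the Treg count named in the null.

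**Step 2: 7/25 v 2/25.** With a and b events in arms of 25, Pearson chi-square = 50 × [a(25−b) − b(25−a)]² / [25 × 25 × (a+b) × (50−a−b)].

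- Chi-square = 50 × (161 − 36)² / (625 × 9 × 41) = 781,250 / 230,625 = 3.39, P=0.066. Yates and Fisher both give 0.14.
- Expected events per arm are 9/2 = 4.5, below 5.
- Risk difference = 0.28 − 0.08 = +0.20.
- Wilson limits are 0.143 to 0.476 (AZD1656) and 0.022 to 0.250 (placebo).
- Newcombe lower limit = 0.20 − √[(0.28 − 0.143)² + (0.250 − 0.08)²] = −0.02.
- Newcombe upper limit = 0.20 + √[(0.476 − 0.28)² + (0.08 − 0.022)²] = +0.40.

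The test says only not significant. The interval says that anything from a 2-point reduction to a 40-point excess is compatible with the data.

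**Step 3: 6/25 v 1/25.** The risk difference is again +0.20.

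- Chi-square = 50 × (144 − 19)² / (625 × 7 × 43) = 781,250 / 188,125 = 4.15, P=0.042.
- Yates gives 0.103 and Fisher 0.098. Expected events per arm are 3.5.

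The same 20-point difference is significant here and not in Step 2, and here the result turns on a choice of test that the text leaves open. With equal arms of 25, every table with 9 or fewer events in total has a smallest expected count below 5.

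**Step 4: two further illustrations.** 5/25 v 2/25 gives P=0.22 and +12 points (Newcombe 95% CI −8 to +32). For 0/25 the exact upper limit is 1 − 0.025^(1/25) = 13.7%.

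**Step 5: power at 25 per arm.** All 26 × 26 tables were enumerated and the probabilities of those with P<0.05 were summed.

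| Assumed placebo risk | AZD1656 risk | Chi-square (uncorrected) | Fisher |
|---|---|---|---|
| 5% | 15% | 21% | 7% |
| 10% | 20% | 17% | 9% |
| 10% | 30% | 45% | 30% |
| 15% | 45% | 67% | 53% |
| 20% | 40% | 35% | 23% |
| 20% | 60% | 87% | 79% |

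Over these assumed baselines, power to detect a tripling runs from 21% to 87% with chi-square.

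**The case against.** The sentence in 19.6 is very probably a drafting slip. A chi-square test on rejection tests rejection whatever 19.6 says. This stands: a reader might infer that the misworded null is what could hide a rise in rejection, but it is not. That risk comes from the small sample and from reporting a P-value alone.

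A reader might also take 11.5 as making the P-value the answer to the safety question. The documents do not support that. Section 11.5 names no test or decision rule, and nowhere is P>0.05 equated with no difference or with safety. The most that can be said is that the text has no safeguard against that reading.

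Nor do the documents assign chi-square to AE or SAE counts. Section 11.5 asks for number and type, and hypoglycaemia and infections are labelled descriptive in 11.3.2.

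Incidences by arm are the endpoints themselves, so event rates can be expected in the report, and an interval could be calculated from them afterwards. This also stands. What is missing is a prior commitment to the interval, and a choice of method for small counts.

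Low power is normal in a pilot sized for feasibility, and the fix does not raise it. The power figures are therefore not a reason to enlarge the trial. They show why a non-significant result should not stand alone. Finally, the cited SAP may already give estimates and intervals. If so, the second problem shrinks to aligning the protocol with it, but 19.6 would still need correcting.

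**Conclusion.** The point holds in two separate parts. First, 19.6 is wrong as written for the six tested secondary endpoints; the practical consequence is small and the correction is plain. Second, the protocol text gives delayed graft function and rejection a chi-square P-value and nothing else, which is uninformative at 25 per arm and unstable when events are few. A 20-point difference can fall on either side of 0.05, and at 6 v 1 the choice between uncorrected chi-square and Fisher decides which.

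This rests on the following: rejection is analysed as patients with at least one event (11.5 supports this, although 11.3.2 speaks of episodes); the arms are 25 and 25, although 13.4.1 describes simple and 13.4.2 blocked randomisation, and undosed patients are not replaced; the placebo rates are assumed; and the SAP was not seen. It is a correction that should be made, but it does not affect the primary analysis.

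**What to change.** 1. Reword 19.6 so that each tested secondary endpoint (1, 2, 3, 6, 7, 8) is compared under a null of no difference between arms in that endpoint, and exempt 4, 5 and 9 as descriptive.
2. For delayed graft function and rejection, make the main result events/patients by arm and the risk difference with a 95% interval. Choose Newcombe or exact in advance. Label any P-value nominal, and use Fisher's exact test when an expected count is below 5.
3. State that the interval takes precedence, since it and the P-value can disagree at the margin: for 6 v 1 the Newcombe interval (0.05 to 39.7 points) just excludes zero while Fisher gives 0.098.
4. State that a non-significant safety or rejection result will be reported with its confidence limits and not described as no difference.
5. Check the SAP and bring the two documents into line.

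The cost is a few sentences, slightly more reporting, and less definite wording on safety. No new data, visits or patients are needed, and power is unchanged.

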19.7 Interim analysis and criteria for the premature termination of the trial

There will be an interim datalock after the last patient has completed visit 7, at which point we will analyse the primary endpoint data and the relevant secondary and tertiary endpoints. There will be a secondary analysis after the final data collection review one year after transplant.

19.8 Subject population

The study population will be those patients undergoing a renal transplant at the RLH renal unit who satisfy the inclusion criteria and do not meet any of the exclusion criteria.

19.9 Procedure(s) to account for missing or spurious data

As this group of patients attend standard of care clinic visits very frequently post transplantation, it is not expected that they will be lost to follow up. The research team will make every effort to rectify any missing or spurious data.

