14.2 Sample Collection/Labelling/Logging

Samples will be collected by the research nurse or trained phlebotomist as per standard of care.

Samples will be labelled with patient identification and sent to the local labs as per routine care and the results logged on the pathology system and transcribed to the CRF.

The only samples that will be sent to the local lab, which are not part of routine care, are for serum C-peptide.

Volume of samples to be collected:

The total volume of blood which will be taken on top of routine care is:

1 table-spoon (approximately 20ml) of blood per clinic visit (4x 6ml samples of blood) in lithium heparin tubes provided locally.

In addition, 20ml of blood will be taken at visit 1, 2, 6 and 7 for Treg quantification via FACS. This sample will be taken to the Royal London Immunology laboratories by members of the study team for processing.

Any biopsy material will be processed and stored as part of routine clinical care.

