14.4 Sample Analysis Procedures

All standard (biochemistry, haematology) samples will be taken to the local lab by the research nurse/team after being taken. All samples will be processed in accordance with local procedures.

In addition, research blood samples will be taken at the same time, labelled with the patient's study number. The isolation and FACS analysis of peripheral blood cells will be performed by members of the study team as per the Immunology lab's standard SOPs.

Peripheral blood cell samples and stored serum may also be taken to the William Harvey Research Institute by members of the study team, for functional analysis of peripheral T cell populations and analysis of inflammatory signalling markers. After sample processing is completed the samples will be destroyed and not stored further.

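### The primary Treg comparison is labelled ITT, but the tests named in 19.5 use only patients with both the visit-1 and visit-6 counts, and 19.9 gives no rule for a count that stays missing

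*Combined protocol and SAP*

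**What the plan says.** Section 19.9, on missing or spurious data, rests on attendance. Patients come to standard-of-care clinics very often after transplant, so "it is not expected that they will be lost to follow up". It then says: "The research team will make every effort to rectify any missing or spurious data". It names no statistical method, rule or sensitivity analysis for a value that stays missing.

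The primary endpoint (11.3.1, 19.3) is the change in peripheral Treg number from baseline to 3 months by flow cytometry. Section 14.2 lists this blood as additional to routine care: "In addition, 20ml of blood will be taken at visit 1, 2, 6 and 7 for Treg quantification via FACS". The schedule in 13.7.1 agrees. Visit 1 is the randomisation visit, up to 24 hours after transplant. Visit 6 is week 12, within a week either side. Visit 7 is two weeks after study drug stops.

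Section 19.5 sets the analysis. On the set: "The endpoint data will be analysed on an ITT basis, with no subgroup analysis". On the quantity: "change in mean Treg cell number between baseline and month 3 between the 2 groups". On the test: "Statistical analysis will be by student t-test (unpaired) or Mann-Whitney U test".

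Three other passages bear on who has a count:
- 13.8: a patient may decline further study visits and still be followed by the clinical team.
- 13.8 and 15.15: patients taken off study drug continue the other study activities.
- 13.4.1: a patient randomised but never dosed is left out of the study and not replaced.

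**The concern.** The reassurance in 19.9 holds for measurements that the clinic makes anyway, such as creatinine and HbA1c. It does not carry over to the primary endpoint. A patient can be fully present in routine follow-up, so not lost in the sense of 19.9, and still have no month-3 Treg count. A baseline count missed before dosing cannot be replaced later, and visit 7 is off drug, so it does not stand in for month 3.

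What is at stake is precision and the meaning of the comparison. With 25 per arm and no allowance for loss (19.1), each incomplete pair removes a patient from the primary test. If missing counts are related to the early clinical course or to willingness to attend, the comparison among completers is also exposed to bias, whatever it is called. The week-1 count, already collected, plays no part in the primary test although it carries information about patients whose month-3 count is missing.

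**Working it through.** **Plan's own figure.** There is none to reproduce. Section 19.1 sets 25 per arm on feasibility, without power, effect size, SD or missing rate.

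**Inputs**
- From the documents: 25 per arm (19.1); significance at 5% (19.5), taken as two-sided because sidedness is not stated; Treg draws at visits 1, 2, 6 and 7 (13.7.1, 14.2).
- Assumed: 80% power; fraction missing at baseline m1 = 4%, 8% or 12%, paired with month 3 m6 = 8%, 12% or 20%; independent losses, missing completely at random; visit-2 missing rate between m1 and m6; equal visit variances; equal correlation r between visits, 0.4 to 0.7.

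**Step 1: patients with a change score.** N = 50 x (1 - m1) x (1 - m6).
- 50 x 0.96 x 0.92 = 44.2
- 50 x 0.92 x 0.88 = 40.5
- 50 x 0.88 x 0.80 = 35.2

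**Step 2: detectable difference, complete cases.** The normal approximation is d = sqrt(2/n) x (1.960 + 0.842). At n = 25 per arm, d = 0.283 x 2.802 = 0.79 SD of change. With the noncentral t distribution:

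| Per arm | Detectable difference (SD of change) |
|---|---|
| 25 (no loss) | 0.81 |
| 22 (4%/8%) | 0.87 |
| 20 (8%/12%) | 0.91 |
| 17.6 (12%/20%) | 0.97 |

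**Step 3: variance of the month-3 difference under three analyses.** Take unit variance at each visit, and let n be the complete pairs per arm.
- Complete-case change: 2 x 2(1 - r)/n.
- Complete-case ANCOVA: 2(1 - r^2)/n.
- Repeated-measures model on visits 1, 2 and 6 with a common baseline mean: for each pattern of observed visits, form X'V^-1X from the rows seen. Weight by the pattern's probability, sum over both arms and invert. The variance of the month-3 contrast is read from the inverse, with the covariance treated as known.

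The ratio of ANCOVA to change is (1 - r^2)/[2(1 - r)] = (1 + r)/2, whatever the missing rate. That is 0.70 at r = 0.4 and 0.85 at r = 0.7, so adjusting for baseline alone saves 30% and 15%.

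| Missing (baseline/month 3) | r | Model vs change | Model vs ANCOVA |
|---|---|---|---|
| 4%/8% | 0.4 | 33% lower | 4% lower |
| 4%/8% | 0.7 | 18% lower | 4% lower |
| 8%/12% | 0.4 | 35% lower | 8% lower |
| 8%/12% | 0.7 | 21% lower | 7% lower |
| 12%/20% | 0.4 | 38% lower | 12% lower |
| 12%/20% | 0.7 | 24% lower | 10% lower |

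Most of the gain over the stated analysis is baseline adjustment. The last column is the part due to keeping incomplete patients and using week 1.

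**Bias.** The documents give nothing from which to quantify bias from outcome-related missingness.

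**The case against.** A reader might go further. Because 14.4 says "After sample processing is completed the samples will be destroyed and not stored further", it is tempting to infer that a missed or failed run can never be recovered. The documents do not support that. Destruction has no bearing on a draw that was never taken. Section 14.1 has cells isolated and stored, and 14.4 destroys them only once processing is finished, so a failed run may be repeatable. A missed visit-6 draw can be retaken within the existing window of one week either side. Laboratory SOPs, which 14.4 cites, may hold re-run rules.

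Other points against the concern are fair:
- No passage says that patients without both counts are dropped; this is inferred from the named tests and the absence of a rule.
- Section 19.3 refers to a SAP for full details. That text is not available here and may contain a rule.
- Visit 1 combines the draw with randomisation and dispensing, while patients are in hospital (9.2), so missed baselines may be few.
- Stopping study drug does not by itself end Treg sampling (13.8, 15.15).
- Source data verification (20.7) and regular monitoring (22.1) can find spurious values before datalock.
- The trial is a pilot with no stated power to lose.

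These points lower the likely amount of missing data and remove any claim that recovery is impossible. They do not supply a rule for the counts that remain missing, and they do not change what a two-group test on change can use.

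**Conclusion.** The concern holds in limited form. The attendance argument in 19.9 does not protect the primary endpoint, and the tests in 19.5 default to complete cases under an ITT label. The label is also at odds with 13.4.1, which leaves out randomised but undosed patients.

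The size is moderate and conditional. Across the assumed missing rates, the complete-case detectable difference rises from 0.81 SD to about 0.87-0.97 SD. The proposed model would cut variance by about 18-38% against complete-case change, but by only about 4-12% against complete-case ANCOVA. These figures assume data missing completely at random, equal visit correlations and a known covariance, so they are a guide rather than a forecast. No figure stated in the plan is shown to be wrong. The conclusion would need revisiting if the separate SAP contains a missing-data rule.

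**What to change.** 1. In 19.5, make the primary estimate the month-3 Treg difference from a likelihood-based repeated-measures model on visits 1, 2 and 6, with a common baseline mean and on the log scale if counts are skewed. Every patient in the analysis set with any Treg count then contributes, including counts taken after study drug was stopped. Visit 7 stays out because it is off drug.
2. Keep the complete-case Mann-Whitney test on change as a sensitivity analysis.
3. In 19.9, state this handling of missing counts and report the number missing by visit and arm, with reasons.
4. Define the analysis set so that the ITT label in 19.5 and the exclusion of undosed patients in 13.4.1 agree.
5. Optionally, hold any residual cells until queries at the first datalock are closed, and flag any re-run count.

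The cost is wording in the protocol and SAP, plus a little freezer space if item 5 is adopted. No visit or blood draw is added. The downside is that the model assumes data missing at random and approximate normality with 50 patients, which is why item 2 is kept.
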